**1) Protocol Abstract** (*Briefly (in 250 words or less) describe the study in language understandable to a layperson. Include a brief description of the study purpose, target disease/condition if applicable, key eligibility criteria, and main study interventions*): Each year in the United States 550,000 people develop upper-extremity movement deficits after stroke (hemiparesis). The recent success of mirror therapy (MT) is notable because it is a simple treatment for hemiparesis, and may be feasible for home use. MT uses a standard mirror to create a compelling illusion in which movements of the unimpaired limb appear as if they are being made by the impaired limb. We propose to complete a randomized placebo-controlled clinical trial of home-based MT with a target enrollment of 100 chronic stroke patients. The therapy will consist of a standardized set of hand, wrist, and elbow movements completed in two daily 30-minute sessions, 5 times per week for 4 weeks. Patients assigned to the placebo treatment (identical therapy with an opaque divider rather than a mirror) will be crossed over to receive MT after a three month follow-up. The therapy will be performed by the participant within his/her home. This project will have two phases. The first phase, to be completed at Einstein, will include all of the behavioral testing. The second phase, to be completed at the University of Pennsylvania, will be limited to MRIs and CTs and will be completed under a separate IRB protocol at the University of Pennsylvania with [name] at the site PI.

**2) Project Objectives and Hypotheses:** The first goal of the study will be to determine whether a home-based form of MT is an effective treatment of hemiparesis. The second goal will be to determine the optimal dosing of MT by including weekly measures of improvement. The third goal will be to understand individual differences in the efficacy of mirror therapy. Previous MT studies have not reported, or lacked the power to test, why some patients benefit from MT and others do not, even though significant individual differences have been reported. Our use of a large sample of patients will allow us to assess predictors of therapeutic benefit.

Albert Einstein Healthcare Network <hr/> Einstein	AEHN Protocol/Summary		
	NUMBER	DATE	PAGE
	HRP-204	11/1/2011	2 of 27

**3) Background/Significance of Research (Provide the scientific or scholarly background and rationale for the research based on the existing literature (include references). Describe relevant prior experience and gaps in current knowledge. Describe any relevant preliminary data. Explain the significance of the research in terms of why it's important and how it will add to existing knowledge.):**

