assigned to the placebo treatment (identical therapy with an opaque divider rather than a mirror) will be crossed over to receive MT after a three month follow-up. To date 7 patients have completed the proposed therapy regimen in a pilot study, and overall the results were encouraging. Patients showed an average improvement (relative to baseline) of 27% and 24% on the Wolf Motor Function test and Jebsen Hand Function test, respectively, two functional tests of simulated ADL performance. Even greater improvements were observed at the impairment level, with average improvement on grip force, pinch force, and finger tapping being 63%, 58%, and 43%, respectively. If the results of the full trial match those of the pilot study, home-based MT would be a meaningful advancement in the cost of hemiparesis rehabilitation.

Reduced medical costs could also come from more efficient therapist utilization. Because the therapeutic benefits of rehabilitation often decrease over time, it would be worthwhile to know the balance between treatment dosing and treatment benefit. To date little is known about the dosing of MT because only one study [18] has measured therapeutic benefit at multiple time points during treatment (in contrast to only before and after 4 or 6 weeks of treatment in previous RCTs [15, 20, 21]). Stevens and Stoykov [18] reported that two chronic stroke patients given 12 1-hour sessions of MT improved most rapidly after 3 sessions (the first assessment point) and showed relatively minor improvement in the following 7 sessions (the second assessment point). These case studies suggests that reducing dosage of MT could still lead to a clinically significant improvement in functioning. The proposed study would inform the issue of MT dosing by measuring outcomes after each week of treatment in a large sample of patients. Our pilot study results indicate that most of MT's therapeutic benefit may occur within the first two weeks of treatment. In this study we administered three impairment level tests (grip force, pinch force, finger tapping) as well as the Jebsen test after each week of therapy. Average improvement was 21%, 44%, 46%, and 47% for weeks 1-4, respectively. Although additional data are clearly needed to further support this claim, these initial results suggest that reduced therapy dosing may be nearly as therapeutic as longer courses of treatment.

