#### C.7. THERAPY REGIMEN

**a. Group assignment:** A research assistant (RA), who will not be involved in any assessments, will assign patients to the MT or placebo therapy (identical therapy with an opaque divider rather than a mirror) using stratified randomization based on the patient's Fugl-Meyer score. Before starting the trial an assignment order will be developed based on whether a patient's pre-treatment Fugl-Meyer score was low (between 10 and 30) or moderate (between 30 and 50). A previous MT RCT using a similarly chronic patient population and an identical placebo therapy showed little benefit of the placebo therapy. Thus, we must consider a balance between the scientific requirements of an appropriate control group and the ethical considerations of using patients' time to complete a therapy that is known to be ineffective. To balance these considerations, we will assign patients to the MT and placebo treatment groups in a 2:1 ratio, respectively. This inequality in sample size will only reduce statistical power by approximately 3% [81]. In addition, patients assigned to placebo treatment will be given the option of being crossed over to receive MT after the three month assessment. Patients will not be aware of which therapy is the placebo because both therapies will be described as studying the role of visual feedback rather than a test of "mirror therapy." Both treatments will include 2 daily 30 minute

Albert Einstein Healthcare Network <hr/> Einstein	AEHN Protocol/Summary		
	NUMBER	DATE	PAGE
	HRP-204	11/1/2011	12 of 27

therapy sessions, 5 days per week over a 4 week period.

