**C.12. Testing Specific Aim 2 (optimal treatment dosing)**

Optimal treatment dosing will be examined by expressing each primary outcome measure's average value at the three mid-treatment assessments and the three-month post-treatment assessment as a percentage between pre-treatment (0%) and immediate post-treatment (100%) assessments. This information could then be used in clinical decision-making when determining whether the magnitude of change expected in a given time period would be "worth" the additional treatment time or whether that addition time would be better spent trying another therapy. Inferential tests will not be used because of the problem of being unable to detect "non-significant" differences between two time points as well as the possibility that the large sample size will be able to detect statistically-significant differences across adjacent time points even though the clinical significance of the differences' magnitudes are questionable.

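### Aim 2 promises the optimal dosing of mirror therapy, but a single 4-week course supports only a description of improvement within that course

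*Combined protocol and SAP*

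**What the plan says.** Section 2 (Project Objectives and Hypotheses) sets the aim: "The second goal will be to determine the optimal dosing of MT by including weekly measures of improvement". The heading of C.12 also speaks of optimal treatment dosing.

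The course is the same for everyone. C.7.a reads "Both treatments will include 2 daily 30 minute" and, across the page break, "therapy sessions, 5 days per week over a 4 week period". Only the type of therapy is randomised: "we will assign patients to the MT and placebo treatment groups in a 2:1 ratio, respectively", from a "target enrollment of 100 chronic stroke patients" (section 1).

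C.8 places three mid-treatment assessments of the primary outcomes before therapy days 6, 11 and 16, by assessors who do not know the group. C.9 adds assessments 1 day and 3 months after the final session.

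C.12 expresses the average of each primary measure at the mid-treatment and 3-month visits "as a percentage between pre-treatment (0%) and immediate post-treatment (100%) assessments", without inferential tests. It suggests that clinicians could use the result to judge whether more treatment time is worthwhile or "whether that addition time would be better spent trying another therapy". In A.2 the pilot results are introduced with a caveat that more data are needed, and then: "these initial results suggest that reduced therapy dosing may be nearly as therapeutic as longer courses of treatment".

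**The concern.** Choosing a course length requires knowing what patients have gained when they stop and what they still have some time later. The design observes the first at several points and the second at only one, after 4 weeks. An early plateau while therapy continues is compatible with good retention after a shorter course and also with poor retention. If the plateau were reported as a finding on optimal dosing, clinicians could read it as support for a shorter course that the trial had not followed up.

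A second, smaller problem concerns reporting. C.12 asks the reader to weigh the size of change expected over a period, but presents the weekly results on a scale from which size has been removed.

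**Working it through.** No sample size, test or threshold is given for Aim 2, so there is no planned figure to reproduce. The check sets the visit schedule against the aim and then examines the scale.

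**1. What is observed for each course length.** Two sessions a day for 5 days is 10 sessions a week, or 40 in 4 weeks (section 6.a.ii also counts 40).

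| Amount of therapy | Status at about that point | Status 3 months after stopping there |
|---|---|---|
| 1 week, about 10 sessions | Yes, before day 6 | No |
| 2 weeks, about 20 sessions | Yes, before day 11 | No |
| 3 weeks, about 30 sessions | Yes, before day 16 | No |
| 4 weeks, 40 sessions | Yes, 1 day after | Yes |
| More than 4 weeks | No | No |

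The missing cells are not filled elsewhere. The optional crossover of placebo patients to mirror therapy is described without any other course length. Section 6.i.ii ends data collection when a participant withdraws, and section 8 says the duration of benefit is not known.

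**2. The C.12 scale on the pilot data.** With M0 the pre-treatment mean, Mk the mean at week k and M4 the immediate post-treatment mean, the scale is 100 × (Mk − M0)/(M4 − M0). The pilot figures in A.2 are already improvements from baseline, so M0 = 0:

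- week 1: 21/47 = 44.7%
- week 2: 44/47 = 93.6%
- week 3: 46/47 = 97.9%
- week 4: 47/47 = 100%

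The weekly gains are 21, 23, 2 and 1 points, so the scale does show flattening within the course. These are averages over grip, pinch, finger tapping and the Jebsen test in 7 patients. None of those is a primary outcome, so the figures illustrate the scale and do not forecast the trial's curve.

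**3. What the scale removes.** Multiplying every change by a constant leaves the percentages unchanged:

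- total gain 47%: 21, 44, 46, 47
- total gain 10%: 4.47, 9.36, 9.79, 10
- total gain 1%: 0.45, 0.94, 0.98, 1

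All three give 44.7, 93.6, 97.9 and 100%. C.11 analyses the two post-treatment visits only, so no planned analysis reports weekly change in original units.

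**4. A purely illustrative retention example.** The documents give no retention figures; those here are assumed. Suppose the 4-week course keeps 80% of its gain at 3 months.

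- If a 2-week course also kept 80% of its gain: 0.936 × 0.80 = 0.75 of the immediate 4-week gain, and 0.75/0.80 = 94% of what the 4-week course keeps.
- If it kept 40%: 0.936 × 0.40 = 0.37, and 0.37/0.80 = 47%.

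The trial's data would be identical in both cases. The example shows that the data cannot separate them; it does not say which is likelier.

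**5. Whether comparing course lengths is realistic at this size.** At 2:1, about 100 × 2/3 = 67 patients receive mirror therapy, or 33 for each of two course lengths. The detectable difference at 80% power and two-sided 5% is (1.96 + 0.84) × √(2/33) = 0.69 SD. Showing a shorter course non-inferior (one-sided 2.5%, 80% power, no true difference) needs 2 × (1.96 + 0.84)²/margin² per arm: 63, 175 or 393 for assumed margins of 0.5, 0.3 or 0.2 SD. Narrowing the aim is therefore the practical repair.

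**The case against.** A reader might infer that a shorter course cannot be judged at all. The documents do not support that. The assessments before days 6, 11 and 16 are made by assessors unaware of group, in patients at least 6 months after stroke and no longer in upper-extremity therapy. They show roughly what a patient stopping then would show that day. Only persistence is unobserved.

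A reader might also blame the 100% anchor for hiding gain beyond week 4. It is not the cause. The scale is a linear rescaling, and gain beyond week 4 is unseen because nobody is treated beyond week 4; raw units would have the same limit. The 3-month value is not capped and may fall below or exceed 100%. A late plateau could hint at little further gain, but that is extrapolation.

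The defence is also right that the documents are cautious. C.12 is declared descriptive and says only that the information could be used. The A.2 remark concerns the pilot and carries a caveat. Absolute effect at 1 day and 3 months is addressed by the C.11 ANCOVA. It would be wrong to say that the plan has no measure of absolute benefit, or that it already asserts lasting benefit from a shorter course.

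Two things still stand. Section 2 and the C.12 heading promise optimal dosing, which the schedule cannot deliver. And C.11 does not cover the weekly visits, whose size C.12 asks the reader to weigh.

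**Conclusion.** The point holds in limited form. Aim 2 can describe immediate status after 1, 2 and 3 weeks within one 4-week regimen. It cannot establish an optimal dose, the lasting benefit of a shorter course, or the effect of a longer one. This follows from the visit schedule alone and needs no numerical assumption.

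The loss of absolute size on the C.12 scale is also exact: gains differing 47-fold give one curve. It is a reporting gap, since the raw weekly scores are collected.

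The 94% versus 47% contrast is not an estimate of the harm. It rests wholly on assumed retention of 80% and 40% and on a 7-patient pilot average of measures that are not primary outcomes; with equal retention the 94% reading stands. Aim 1 is unaffected. The change is worth making because it is nearly free and prevents a dosing conclusion that the data would not support.

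**What to change.** - In section 2 and in the heading and text of C.12, restate Aim 2 as describing the time course of improvement during a 4-week course of mirror therapy.
- In C.12, state that the 3-month result applies to the 4-week course only, and that no inference is drawn about the lasting benefit of a shorter course or about any effect of a longer one.
- In C.12, report the weekly and 3-month mean changes from pre-treatment in each primary measure's own units beside the percentages.

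The cost is a second aim less ambitious than the one now stated, some rewording and one extra table column. Therapy, visits and patient numbers do not change. The added column makes absolute size visible; it does not supply information about courses that nobody receives, so the wording change is needed as well.

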**A.1. Hemiparesis in patients with stroke**

Every year 550,000 people in the United States develop problems making arm and hand movements because of a stroke. Of those with deficits, 30% - 60% fail to ever recover adequate usage of the limb [1]. The consequences of these impairments are profound, and stroke patients rate the return of upper-extremity functioning as a high priority [2]. Motor deficits also lead to negative psychological and social outcomes such as depression and withdrawal [3]. Beyond the impact on individuals, stroke patients place a significant burden on the health care system, with stroke-related medical and disability costs totaling \$62.7 billion each year in America alone [4].

Motor deficits in stroke patients are most clearly observed in the limb opposite the lesioned hemisphere (hemiparesis) and affect the distal portions of the limb such as the hand more significantly than proximal portions such as the shoulder [5]. Previous studies show that these deficits are caused by damage to the corticospinal tract, including the primary motor cortex and internal capsule, as well as cortical areas such as the premotor and supplementary motor areas [6, 7]. In addition to motor production problems, non-motor deficits such as poor limb sensation and pain contribute to limited use of the paretic limb [8]. Treating these motor and non-motor deficits is especially difficult in chronic patients [1]. Improvement for most chronic patients is also hindered by limited medical insurance coverage for long-term therapy, leading many to receive little to no therapy in the chronic stage.

Empirically validated treatments for hemiparesis are varied and include strength training [9], functional task practice [9], bilateral training [10] and electrical stimulation [11]. To date, the single therapy with the greatest amount of empirical validation is constraint-induced movement therapy (CIMT), which combines restraint of the unimpaired limb and intense practice using the impaired limb under the supervision of a therapist (typically 10 6-hour sessions over two weeks [12]). A common feature of almost all of these therapies is that they require a significant amount of therapist involvement, a burden that is becoming increasingly problematic due to cost concerns. Motivated by the decreasing availability of therapist time, there has been considerable recent interest in the use of robotic training to both reduce reliance on therapists as well as increase the number of movement repetitions within therapy sessions (e.g. [13]). These benefits, however, come at the expense of the significant initial cost to acquire the robotic device.

**A.2. Mirror therapy**

The recent success of mirror therapy (MT) for treating hemiparesis in stroke patients is notable because it does not require a significant investment in equipment. Originally developed as a treatment for phantom limb pain (for review, see [14]), MT involves the patient being seated at a table in front of a vertically-oriented mirror. The patient places her unimpaired arm on the reflective side of the mirror and her impaired arm behind the mirror so that it is not visible. Using this setup, the patient only sees the unimpaired arm in the mirror. However, when the mirror is placed midway between the two limbs, movements of the unimpaired limb (viewed in the mirror) appear in the same location as the impaired limb. Thus, the MT setup creates a compelling illusion in which movements of the unimpaired arm appear as if they are being made by the impaired arm behind the mirror [16].

The illusory visual feedback of the perceived impaired limb moving like the unimpaired limb is the basis for MT's therapeutic benefit. Although only visual feedback is directly modified in the therapy, the results of several case studies [17, 18], a small-sample study without a control group [19], and three randomized control trials with moderate sample sizes (40, 40, and 36 patients; [15, 20, 21]) indicate that MT produces a benefit for stroke patients that is comparable to other therapies. For example, both MT and a briefer version of CIMT produce an approximate 20% increase in FIM score, a common measure of functional independence in activities of daily living (ADLs) and the only outcome measure that has been reported for both therapies [20, 22]. The benefit of MT is especially noteworthy given its methodological simplicity and the potential for use in the home. Informal case studies [17] and one RCT with 20 treated patients [21] have reported improvement in paretic limb functioning with home-based mirror therapy, a finding that is consistent with a recent report that home-based CIMT may be as effective as therapist-administered CIMT [23].

We propose to complete the largest randomized clinical trial of home-based mirror therapy. The therapy will consist of a standardized set of hand, wrist, and elbow movements completed in two 30-minute sessions per day, 5 times per week for 4 weeks. Patients

Albert Einstein Healthcare Network <hr/> Einstein	AEHN Protocol/Summary		
	NUMBER	DATE	PAGE
	HRP-204	11/1/2011	3 of 27

assigned to the placebo treatment (identical therapy with an opaque divider rather than a mirror) will be crossed over to receive MT after a three month follow-up. To date 7 patients have completed the proposed therapy regimen in a pilot study, and overall the results were encouraging. Patients showed an average improvement (relative to baseline) of 27% and 24% on the Wolf Motor Function test and Jebsen Hand Function test, respectively, two functional tests of simulated ADL performance. Even greater improvements were observed at the impairment level, with average improvement on grip force, pinch force, and finger tapping being 63%, 58%, and 43%, respectively. If the results of the full trial match those of the pilot study, home-based MT would be a meaningful advancement in the cost of hemiparesis rehabilitation.

Reduced medical costs could also come from more efficient therapist utilization. Because the therapeutic benefits of rehabilitation often decrease over time, it would be worthwhile to know the balance between treatment dosing and treatment benefit. To date little is known about the dosing of MT because only one study [18] has measured therapeutic benefit at multiple time points during treatment (in contrast to only before and after 4 or 6 weeks of treatment in previous RCTs [15, 20, 21]). Stevens and Stoykov [18] reported that two chronic stroke patients given 12 1-hour sessions of MT improved most rapidly after 3 sessions (the first assessment point) and showed relatively minor improvement in the following 7 sessions (the second assessment point). These case studies suggests that reducing dosage of MT could still lead to a clinically significant improvement in functioning. The proposed study would inform the issue of MT dosing by measuring outcomes after each week of treatment in a large sample of patients. Our pilot study results indicate that most of MT's therapeutic benefit may occur within the first two weeks of treatment. In this study we administered three impairment level tests (grip force, pinch force, finger tapping) as well as the Jebsen test after each week of therapy. Average improvement was 21%, 44%, 46%, and 47% for weeks 1-4, respectively. Although additional data are clearly needed to further support this claim, these initial results suggest that reduced therapy dosing may be nearly as therapeutic as longer courses of treatment.

#### B.1. Understanding individual patient differences in treatment response

A critical, but often understudied, issue in rehabilitation is predicting individual patient differences in treatment response. As reviewed in section A.1, a wide range of therapies exist for the treatment of hemiparesis, and several recent RCTs comparing two active treatments have reported equivalent benefits at the group level [9, 30, 31]. It would be clinically valuable to understand the characteristics of patients who do and do not respond to each therapy given the magnitude of these individual differences. For example, in a recent RCT of MT for chronic stroke patients [20], improvement in the Brunnstrom scale outcome measure ranged from 0% to 33% (estimated from two standard deviation above and below the mean of 16.5% improvement). Information about predicted individual differences would be useful for clinicians when deciding the course of treatment most likely to benefit the patient.

We assert that individual differences in response to MT are predictable through an understanding of the mechanisms responsible for MT's therapeutic benefit. The assembled team composed of researchers trained in the basic science of sensorimotor control ([name]) and its application to stroke patients (Drs. [name], [name], and [name]) is uniquely positioned to address this issue. The project is innovative because it will test competing predictions regarding the mechanism of MT by utilizing individual differences in lesion location and the integrity of four sensorimotor processes that may underlie MT's benefit. As an overview, we will first discuss the four sensorimotor processes that may underlie the mechanisms of MT's benefit (B.2), and then proceed to a summary of the

Albert Einstein Healthcare Network <hr/> Einstein	AEHN Protocol/Summary		
	NUMBER	DATE	PAGE
	HRP-204	11/1/2011	4 of 27

neural substrates that subserve these processes (B.3). Following this will be a discussion of the behavioral tasks we will use as convergent validity tests of the neuroanatomic predictions (B.4). Finally, we will summarize all of these predictions in Table 1.

